Aim 2: Determine the effects of progressive functional resistance training during gait on cortical and spinal reflex excitability of individuals with ACL reconstruction. The goal of Aim 2 is to test the effects of progressive functional resistance training during walking on cortical and spinal reflex excitability in individuals with ACLR. Cortical and spinal excitability will be assessed before, immediately after the intervention, and at 6 months after ACLR. The assessor will be blinded to patients' group assignment.

Motor Cortical Excitability: Motor cortical excitability changes due to functional resistance training will be evaluated using reliable ($ICC \geq .82$) single- and paired-pulse TMS protocols similar to our prior studies. First, the optimal site for eliciting quadriceps MEP (i.e., hotspot) will be determined using a double cone TMS coil, which is specifically designed for stimulating the leg motor cortex. The hotspot will be identified by determining the stimulation location that produces largest and most consistent MEPs. A frameless stereotaxic coil tracking system will be used to assure consistent placement of the coil during the experiment.^{42,43} Active motor threshold will then be established during a slight background contraction (~5% MVIC) by determining the lowest stimulus intensity that elicits an $MEP > 100\mu V$ in at least 5 of 10 consecutive trials.⁴⁰ Recruitment curves will be created by measuring motor evoked potentials (MEPs) and evoked torque responses of the quadriceps muscle over a range of TMS intensities (70% to 140% AMT). The intervention-mediated changes in cortical excitability will be assessed by examining the changes in MEP/torque amplitudes and slopes of recruitment curves obtained using Boltzmann equation. In cases where sigmoidal relationship is not appropriate ($R^2 < 0.80$), other fits (e.g., linear) will be used as appropriate.

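### The named single-pulse TMS measures can lose or reverse a threshold change if AMT is re-determined at each visit, and the poor-fit rule mixes two kinds of slope (minor; tertiary outcome)

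*Combined protocol and SAP*

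**What the plan says.** All of this is in the combined protocol and SAP, mostly under Motor Cortical Excitability.

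- **Threshold.** "Active motor threshold will then be established during a slight background contraction", by "determining the lowest stimulus intensity that elicits an" MEP above 100 microvolts in at least 5 of 10 consecutive trials.
- **Recruitment curves.** MEPs and evoked torque are recorded "over a range of TMS intensities (70% to 140% AMT").
- **Measures of change.** "The intervention-mediated changes in cortical excitability will be assessed by examining the changes in MEP/torque amplitudes and slopes", the latter being "slopes of recruitment curves obtained using Boltzmann equation".
- **Poor fits.** When R2 is below 0.80, "other fits (e.g., linear) will be used as appropriate".
- **Other TMS.** The section opens by naming "single- and paired-pulse TMS protocols similar to our prior studies", with ICC of at least .82. It defines no paired-pulse measure and does not say which TMS measure the ICC describes.
- **Visits.** Under Aim 2: "Cortical and spinal excitability will be assessed before, immediately after the intervention, and at 6 months after ACLR".

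The plan does not say whether AMT is set once or at each visit, whether the curves are fitted against %AMT or absolute stimulator output, or how a slope from another fit is made comparable with a Boltzmann slope. Study Design for ACLR subjects lists cortical excitability as tertiary. Hypothesis 2A predicts a greater change in corticospinal excitability with resistance training, and Hypothesis 2B uses corticospinal change as a correlate of strength and activation.

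**The concern.** **Threshold.** A lower threshold is one form of greater excitability. If every visit's intensities are multiples of that visit's own AMT, the yardstick moves with the quantity being measured. The MEP at 100% AMT is then held near 0.1 mV at every visit by the definition of AMT, and nearby points are constrained too. A real training effect on threshold could appear as no change or as a small loss. Randomization does not recover it, because a signal removed in every patient cannot show up between arms.

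**Slope.** A Boltzmann peak slope is the steepest point of the curve; a straight-line slope is an average over the tested range. A patient whose fit type differs between two visits shows a change in slope even when nothing has changed.

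**Working it through.** The plan gives no effect size, SD or sample size for this outcome, so there is no figure of its own to reproduce. From the plan: the AMT criterion (0.1 mV), the 70-140% range, the R2 cut-off of 0.80 and the ICC of at least .82. Every curve parameter below is an assumption.

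**1. Threshold change**

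Curve: y = M / (1 + exp((S50 - x)/k)), with x in % of stimulator output and peak slope M/(4k). Assumed M is 0.5, 1 or 2 mV and k is 2 to 6. S50 is set so that y = 0.1 mV at AMT, which gives S50 = AMT + k ln(M/0.1 - 1).

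Worked example: M = 1, k = 4, AMT falling from 45 to 40, as a parallel shift.
- Before: S50 = 45 + 4 ln 9 = 53.8. At 120% AMT (x = 54), y = 51% of maximum.
- After: S50 = 48.8. At 120% of the new AMT (x = 48), y = 45%. At the original intensity (x = 54), y = 79%.

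A rise from 51% to 79% at a fixed intensity is therefore recorded as a fall from 51% to 45%.

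MEP amplitude over the whole grid, parallel shift (k fixed):

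| AMT change | 100% of own AMT | 120% of own AMT | original 120% intensity |
|---|---|---|---|
| 45 to 43 | 0% | -1% to -7% | +3% to +36% |
| 45 to 40 | 0% | -3% to -16% | +4% to +93% |
| 45 to 38 | 0% | -4% to -23% | +4% to +133% |

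If instead S50 and k both scale by 40/45, every MEP amplitude at a given % of own AMT changes by exactly 0%, while amplitude at the original 120% intensity rises by 4% to 128%.

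Peak slope depends on the fitting axis (AMT 45 to 40):

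| | Fitted against %AMT | Fitted against absolute output |
|---|---|---|
| Parallel shift | 40/45 - 1 = -11.1% | 0% |
| Proportional scaling | 0% | 45/40 - 1 = +12.5% |

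Slope therefore loses or reverses the change on a %AMT axis. On an absolute axis it is unchanged by a parallel shift and moves in the right direction under scaling.

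**2. Two kinds of slope**

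Intensities 70, 80, ..., 140% AMT, S50 100-120 and k 5-15 (in % AMT), no noise. The ratio of the least-squares linear slope to M/(4k) runs from 0.31 (S50 120, k 5) to 0.77 (S50 105, k 15). For example, with S50 110, k 8 and M = 100, the peak slope is 100/32 = 3.13 and the linear slope is 1.63, a ratio of 0.52. A wider grid (S50 100-130, k 5-20) gives 0.22 to 0.84.

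How often would a switch occur? Simulation: 4,000 patients at two visits, no true change, between-patient log-SD of the maximum 0.5, three sets of fit bounds (tight, medium, wide).

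| Proportional noise | ICC of log slope (tight/medium/wide) | Sessions with R2 below 0.80 | Variance of slope change, switching / Boltzmann only |
|---|---|---|---|
| 10% | .95/.95/.95 | 0.0% | 1.00 |
| 15% | .91/.90/.86 | 0.1% | 1.02/1.02/1.02 |
| 20% | .85/.82/.74 | 1.8% | 1.14/1.12/1.07 |

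If the stated ICC of at least .82 covers log slope, compatible noise is at most about 20% (tight or medium bounds) or 15% (wide). In that range:
- 0-2% of sessions switch, and 0-3% of patients have different fits at two visits.
- At 20% noise, the median spurious slope ratio in those patients is about 0.46 or 2.0-2.1, depending on which visit switches.
- The variance of slope change rises by 0-14%.
- At most about 0.02 is lost from a Hypothesis 2B correlation assumed to be 0.70.

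With additive noise of 7% of the maximum (ICC .90-.91), no session switches.

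**The case against.** The strongest reply is that the threshold point rests on silence. The plan does not say that AMT is re-set, and if baseline intensities are reused the point falls away. Scaling to threshold can also be a deliberate choice to measure gain and not threshold. AMT is recorded under the stated procedure and is not excluded from analysis. All of this stands, and it is why the point is conditional. What remains is that AMT is a step of an assessment made at three visits, so re-determination is the natural reading, and under it the plan names no measure that shows threshold directly.

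A reader might infer several stronger things that the documents do not support:

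- *Both named measures are blind to threshold.* The 70-140% range gives the stimulus intensities, not the fitting axis. The effect on slope needs a %AMT axis as a second unstated condition. The pinning applies to MEPs; evoked torque loses the change in this way only if its curve shifts with the MEP curve.
- *Amplitudes and slopes are the only TMS evaluation.* Paired-pulse protocols are named too, although no measure is defined.
- *The fit rule could create a false difference between arms.* Randomization and the blinded assessor protect against that. The cost is mainly precision, and MEP and torque amplitudes are untouched by the rule.
- *Many curves will fail the R2 criterion.* Additive noise of 20% of the maximum would put about 25% of simulated curves below 0.80. But additive noise of 10% already gives a slope ICC of .76 to .81, below the stated .82.

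The two calculations also use different curve families: pinning AMT at 0.1 mV implies S50 of 106-139% AMT, against 100-120% in the switching simulation. For later curves (S50 125-140%), 20% noise gave an ICC of about .71 and about 0.1% switching, so the slope point would shrink further.

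**Conclusion.** The concern holds in a limited form and is minor.

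**Threshold.** If AMT is re-determined at each visit, MEP amplitudes at a given %AMT largely lose a threshold change or show it with the wrong sign: 0% or -3% to -16% at 120% of own AMT for an assumed fall from 45% to 40% of output, against +4% to +128% at the original intensity. For slope this also requires fitting against %AMT, and for torque a curve that moves with the MEP curve. The sizes depend on assumed curves. The fixed MEP at 100% of own AMT follows from the plan's own definition of AMT.

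**Slope.** The fallback does combine non-comparable quantities, but noise compatible with the stated ICC makes it rare (about 0-2% of sessions) and the loss small. That rests on the ICC applying to slope, which the plan does not say.

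Both parts concern a tertiary outcome of a pilot trial and bear on Hypothesis 2A and, slightly, 2B. Confidence is medium, because the handling of AMT and the fitting axis are not stated.

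**What to change.** 1. State whether AMT is determined at each visit, which visit's AMT sets the later intensities, and whether curves are fitted against %AMT or absolute output. If AMT is determined at each visit, analyse it in % of stimulator output as an additional tertiary outcome for Hypothesis 2A.
2. Use one slope definition for every session, for example the Boltzmann peak slope M/(4k), for both MEP and torque, with the fit bounds stated. Keep sessions with R2 below 0.80 in the main analysis and examine them in a sensitivity analysis, without substituting another kind of slope. Area under the curve could be added as supportive, but it responds little to a pure steepening and should not replace slope.

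The cost is wording and analysis code, with no new data if AMT is already established at each visit. The downsides are one more tertiary outcome and some poorly fitted slopes in the main analysis.

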Study Design for ACLR subjects: This is a single-center randomized controlled pilot trial of functional resistance training during treadmill walking. Patients with ACLR will be randomized using permuted blocks into one of three groups: 1) functional resistance training with a custom brace during treadmill walking, 2) functional resistance training with elastic bands during treadmill walking, and 3) treadmill walking (sham/control arm). Isometric quadriceps strength symmetry index will be our primary outcome measure. Our secondary outcome measures are: 1) % voluntary activation, 2) knee flexion angle symmetry, 3) knee moment symmetry. Our tertiary outcomes are: 1) patient-reported outcomes via Knee Injury and Osteoarthritis Outcome Score, 2) cortical excitability, and 3) spinal reflex excitability. All outcome measures will be examined at 3 study time points: 1) *Pre-intervention*: about 6 weeks after ACLR (a time-point when adequate quadriceps control is usually achieved), 2) *Post-intervention*: immediately after the intervention, and 3) *Follow-up*: 6-12 months post-ACLR (± 2 weeks) (when patients are typically cleared for return to activity) (Fig. 1).

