H-Reflex Testing: Spinal reflex excitability will be measured with H-reflex testing using a reliable intra- and inter-session protocol ($ICCs > 0.90$)⁵¹ that we have employed previously.^{52,53} Briefly, patients will be positioned supine with the knee supported in flexion and hands at their sides. Factors such as head position, hand movement, etc. may affect the H-reflex so care will be taken to minimize movement. H and M recruitment curves will be mapped for the ACLR limb by applying a 1ms square-wave stimulus to the femoral nerve and recorded using EMG. Stimuli will be delivered by increasing the intensity in 0.2V increments, with a 10-second rest interval after each stimulus until the maximum H-reflex and maximum M-wave are obtained. Three peak-to-peak amplitudes of the maximum H-reflex and M-wave will be recorded and used to create the H-reflex to M-wave ratio.

Analytic Plan: Descriptive statistics will be used to explore the distribution, central tendency, and variation of each measurement, with an emphasis on graphical methods. Normality for each variable will be checked using a Shapiro-Wilks test, and appropriate transformations (e.g., log) will be made when necessary. Linear mixed models will be used to compare the continuous primary and secondary endpoints between the experimental and control arm of the randomized group. Fixed-effects terms will include group, time, group \times time interaction, gender, group \times gender interaction, and other potential covariates such as, age, activity level, and meniscal repair. Patients will be included as random effects in the intercept. A significant main or interaction effect at $\alpha = 0.05$ will be followed by appropriate post-hoc analysis with adjustments for multiple comparisons.

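### Normality is checked on each variable, with no check of model residuals, so the scale of the primary comparison can be chosen after the data are seen, from a test of the wrong quantity

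*Combined protocol and SAP*

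**What the plan says.** All of this is in the Analytic Plan of the combined protocol and SAP, except where noted.

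- Descriptive work comes first. It is meant to "explore the distribution, central tendency, and variation of each measurement, with an emphasis on graphical methods". These plots describe the measurements, not a fitted model.
- The distributional rule is: "Normality for each variable will be checked using a Shapiro-Wilks test, and appropriate transformations (e.g., log) will be made when necessary". Log is the only transformation named. There is no significance level for the test, no list of permitted scales, and no rule by outcome.
- The model follows: "Linear mixed models will be used to compare the continuous primary and secondary endpoints between the experimental and control arm". Its fixed effects include group, time, their interaction, gender, group by gender, and possible covariates. On the random part: "Patients will be included as random effects in the intercept".
- Under Study Design for ACLR subjects, patients are "randomized using permuted blocks into one of three groups" and measured at three time points. The primary outcome there is the isometric quadriceps strength symmetry index, and percent voluntary activation is the first secondary outcome.

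No check of residuals or of random effects is mentioned.

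**The concern.** A linear mixed model assumes that the errors and the patient intercepts are normal around whatever means the fixed effects give. It does not assume that the outcome itself is normal. If the outcome is pooled over arms and visits with different expected means, it is a mixture, and it can fail Shapiro-Wilk when the model is exactly right. Pooled values also include repeated measurements of the same patient, whereas the test assumes independent ones.

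What is at stake is the meaning of the primary result. Hypothesis 1 is about greater improvement, which is a group-by-time contrast, and such contrasts depend on scale. As an illustration with assumed values, gains of 50 to 70 and 60 to 80 are both 20 points, so there is no interaction on the original scale. As ratios they are 70/50 = 1.40 and 80/60 = 1.33, so there is an interaction on the log scale. The symmetry index is already a ratio of legs, so after a log the comparison becomes a ratio of ratios. Different endpoints could also end up on different scales.

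**Working it through.** **Inputs.** Three arms, three visits and a random patient intercept come from the plan. The plan has no figure of its own to reproduce: it gives no mean, SD, sample size or effect size. Visit means, SDs, 10 to 30 patients per arm, the effect size and a 0.05 level for Shapiro-Wilk are therefore assumptions, and ranges are shown.

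**1. False rejection when the model is correct.** Simulated value = visit mean + patient effect + error, both random parts exactly normal, no treatment effect. Share of trials in which Shapiro-Wilk rejects on the raw variable pooled over arms and visits:

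| Visit means | SD between / within patients | 10, 20, 30 per arm |
|---|---|---|
| 50/75/90 | 8 / 6 | 50%, 93%, 99.5% |
| 50/70/85 | 8 / 6 | 15%, 50%, 79% |
| 60/75/85 | 8 / 6 | 3% to 17% |
| 50/75/90 | 12 / 8 | 7%, 19%, 37% |
| 50/70/85 | 12 / 8 | about 3% to 10% |
| 60/75/85 | 12 / 8 | 2% to 4% |
| 50/70/85 | 15 / 8 | about 1% at 10 per arm |
| 70/70/70 | 12 / 8 | 12% to 14% |

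The last row has no time effect; its excess over 5% comes only from repeated values within patients. The same test on residuals or true errors rejects in about 3% to 6% throughout.

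The spread follows from how far apart the means are. With SDs 8 and 6 the total SD is √(8² + 6²) = 10, so 50 to 90 is a shift of 4 SD. With 12 and 8 it is √(12² + 8²) = 14.4, and the same shift is 2.8 SD.

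**2. Test applied visit by visit.** Each test rejects in about 5% of trials. For at least one of three visits, independence would give 1 − 0.95³ = 14.3%; the simulations gave about 11–18%. The plan does not say what happens if visits disagree.

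**3. Type I error.** In a two-arm, two-visit scenario with modest separation, testing first and then taking logs gave 4.8–4.9%, against 4.8–5.0% when always using the original scale. Power loss was 0.2–1.4 percentage points.

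**4. Power in a setting where the test fires often.** Means 50/75/90, SDs 8 and 6, a 7-point effect, two arms compared on change from the first to the second visit.

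- Original scale: SD of change = 6√2 = 8.49, so the standardised effect is 7/8.49 = 0.82. With noncentrality 7/(8.49·√(2/n)) = 1.84, 2.61 and 3.20 at 10, 20 and 30 per arm, power is about 41%, 72% and 88%. Simulation gave 41%, 71% and 88%.
- Log scale, first-order approximation: effect = ln(82/75) = 0.089. Variance of log change ≈ (6/50)² + (6/75)² + (8·(1/50 − 1/75))² = 0.0144 + 0.0064 + 0.0028 = 0.0236, so SD = 0.154 and the standardised effect is 0.58. At 30 per arm, where the test fires in nearly every trial, noncentrality is 0.58·√15 = 2.25 and power about 60%.
- Simulated test-then-log rule: 34%, 45% and 58%.

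The loss arises because log inflates the noise at the low baseline values and turns differences between patients, which cancel in a change score, back into noise.

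**5. Log and a percentage near 100%.** Assume activation follows a beta distribution with mean 90 and SD 6.5. Then a + b = 0.9·0.1/0.065² − 1 = 20.3, so a = 18.27 and b = 2.03. Skewness = 2(b − a)√(a + b + 1)/[(a + b + 2)√(ab)] = −1.10. After log it is −1.40 by simulation. The square root of (100 − activation) has skewness of about 0.24.

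**The case against.** The best defence has four parts.

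- **Pooling is not stated.** A variable may mean the outcome at each visit, and then each test is nearly correct for normal data. This stands. It is why the large rejection rates are conditional, although several visit-wise tests still leave 11–18% with at least one false alarm.
- **The large rates need well-separated means relative to the SDs.** This stands too: moving from SDs 8/6 to 12/8 brings 50/70/85 down from as much as 79% to about 10% at most.
- **The sentence leaves room for judgement.** It asks for suitable transformations if needed, so a rejection does not force a change of scale, and residual checks are omitted rather than forbidden. This is fair to the wording, but unrecorded judgement after seeing the data is the weakness itself.
- **Log is only an example.** It is a natural one for right-skewed measures such as evoked-potential amplitudes. A reader might infer that the plan prescribes log for voluntary activation and so worsens its skew. The text assigns no transformation to any outcome and gives no activation distribution, so that reading is not supported. Calculation 5 shows only what log would do to a left-skewed percentage near 100%. The opening statement's expectation of full activation makes such a shape plausible, not established.

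**Conclusion.** The point holds as a specification weakness of moderate severity. The stated check addresses the raw variables, while the stated model depends on residuals and random effects, and nothing fixes the scale of the primary comparison before the data are seen.

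Its size cannot be pinned down from the documents. Under assumed inputs the false-alarm rate runs from about 1% to over 99% if visits are pooled, and is about 5% per test if they are not. The power loss, up to 30 percentage points (88% to 58%) at 30 per arm, belongs to one assumed setting and assumes that log follows every rejection; in the milder setting the loss was at most 1.4 points.

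A reader might infer that the rule inflates the false-positive rate. The calculations do not show that: type I error stayed near 5%. The harm is an unplanned switch between a difference and a ratio, possible disagreement of scale between endpoints, an undeclared analysis choice and, in some settings, lost power.

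**What to change.** Replace the sentence on normality testing with:

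*The strength symmetry index and the secondary outcomes are analysed on their original scale. Normality and equal variance are assessed graphically on residuals and predicted random effects from the fitted mixed model. If clearly violated, a bootstrap or robust-variance version of the same model, or for % voluntary activation a transformation of the deficit (100 − activation), is reported as a sensitivity analysis.*

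If log is intended for particular tertiary excitability measures, name them now. The cost is SAP wording only: the data, patients and primary model stay the same.

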Study Title: Functional Resistance Training to Improve Knee Function after ACL Reconstruction

NCT Number: NCT03282565

Date: August 13, 2018

The objective of this study is to perform a pilot **randomized clinical trial** that assesses whether progressive functional resistance training during gait will significantly improve quadriceps function, neural excitability, and knee mechanics after ACL reconstruction. We anticipate that this approach will lead to symmetrical quadriceps strength and gait climbing biomechanics, complete voluntary activation, and improved neural excitability and patient-based outcomes.

Aim 1: Determine the effects of progressive functional resistance training during walking on knee outcomes after ACL reconstruction.

Hypothesis 1: Progressive functional resistance training while walking will result in greater improvements in knee extensor strength (primary outcome) than dose-matched treadmill walking. **Hypothesis 1B:** Voluntary activation, sagittal plane knee biomechanics and patient-reported outcomes will also be significantly better after progressive functional resistance training than after dose-matched treadmill training.

Aim 2: Determine the effects of progressive functional resistance training during gait on cortical and spinal reflex excitability of individuals with ACL reconstruction.

Hypothesis 2A: Progressive functional resistance training while walking will result in greater changes in corticospinal excitability than dose-matched treadmill walking. **Hypothesis 2B:** There will be a strong association between changes in knee extensor strength, voluntary activation and corticospinal plasticity.

APPROACH

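### The Analytic Plan does not say how the pre-intervention outcome enters the mixed model and names no primary contrast; on the natural reading it tests a difference in mean change, which is valid but in large samples never more precise than a baseline-adjusted contrast

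*Combined protocol and SAP*

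**What the plan says.** Under Study Design for ACLR subjects, "Isometric quadriceps strength symmetry index will be our primary outcome measure", but no visit is attached to it. The same section says "All outcome measures will be examined at 3 study time points": before the intervention, immediately after it, and at a later follow-up. Three arms are randomised: resistance by brace, resistance by elastic bands, and treadmill walking as control.

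Hypothesis 1 predicts that resisted walking "will result in greater improvements in knee extensor strength (primary outcome) than dose-matched treadmill walking". It gives neither a visit nor an estimator.

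The Analytic Plan is one paragraph. On model terms it says "Fixed-effects terms will include group, time", their interaction, gender and group × gender, then "other potential covariates such as, age, activity level, and meniscal repair". On the covariance it says only "Patients will be included as random effects in the intercept". On testing, "A significant main or interaction effect" at the 0.05 level leads to post-hoc analysis adjusted for multiple comparisons. The comparison is described as one experimental arm against control.

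The plan does not say which visits are responses, whether the pre-intervention outcome is a covariate, whether the arms share a pre-intervention mean, or which test is primary.

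**The concern.** Two things are left open.

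**Handling of the pre-intervention value.** If it is simply a level of time, the group × time term for post-intervention subtracts it with a coefficient of 1. Baseline adjustment lets the data choose that coefficient. When the pre-post correlation is moderate, full subtraction adds noise. The listed covariates do not help: age, gender and meniscal repair do not vary over time, so entered as plain terms they cancel from a within-patient change. The value needed is already being collected.

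**The contrast itself.** Either a main effect or an interaction may open the post-hoc stage. No visit is ranked first, and with three arms it is unclear whether the brace arm, the band arm or both pooled are set against control. These choices could be made after the data are seen. If the group main effect is averaged over all visits, it also includes one at which no treatment effect can exist.

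The documents state "This is a single-center randomized controlled pilot trial" and give no sample size. A small trial has the least precision to spare.

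**Working it through.** **Inputs.** From the documents: three arms, three visits, a random patient intercept, and the 0.05 level (two-sided assumed). The documents give no sample size, SD, effect size or pre-post correlation, so there is no figure to reproduce, and those values are assumed below. The ICC of at least .92 under Knee Strength and Voluntary Activation is test-retest reliability. It is not the correlation between values before and after an 8-week programme, so it is not used.

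**Step 1: what the planned term estimates.** The stated model was fitted to simulated complete data (three arms, three visits, time as a factor, gender and group × gender included). Its group × time coefficient at post-intervention was 1.5626, equal to the difference in mean change. With missing visits the equality is only approximate.

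**Step 2: large-sample variances.** Write S0 and S1 for the pre- and post-intervention SDs, ρ for their correlation and n for patients per arm.

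- Change contrast: 2(S0² + S1² − 2ρS0S1)/n
- Baseline-adjusted contrast: 2S1²(1 − ρ²)/n
- Difference: 2(S0 − ρS1)²/n, which is never negative and is zero when S1 = S0/ρ

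With S0 = S1 the ratio of adjusted to change is (1 + ρ)/2.

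**Step 3: small samples.** Assume 10 per arm, so N = 30 and g = 3 arms. The change contrast has 2(N − g) = 54 degrees of freedom (t = 2.005). Single-visit ANCOVA has N − g − 1 = 26 (t = 2.056) and a variance penalty of 1 + 1/(N − g − 2) = 1.04. The squared CI width ratio is (2.056/2.005)² × 1.04 × (1 + ρ)/2, or about 1.093 × (1 + ρ)/2.

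| ρ (assumed, equal SDs) | Variance ratio, large sample | Cut | Squared CI width ratio, ANCOVA, 10 per arm | Change |
|---|---|---|---|---|
| 0.3 | 0.65 | 35% | 0.71 | 29% narrower |
| 0.5 | 0.75 | 25% | 0.82 | 18% narrower |
| 0.7 | 0.85 | 15% | 0.93 | 7% narrower |
| 0.9 | 0.95 | 5% | 1.04 | 4% wider |

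With 20 per arm the cuts are 32%, 22%, 11% and 1%.

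**Step 4: unequal SDs.** Here the remedies are each compared with the planned change contrast, in large samples, with equal correlations between visits.

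| SDs pre/post/follow-up (assumed) | ρ | Optimal baseline adjustment | Common pre-intervention mean with random intercept only |
|---|---|---|---|
| 1/1.25/1.25 | 0.7 | 2% lower variance | 2% higher |
| 1/1.25/1.25 | 0.8 | no difference | 8% higher |
| 1/1.5/1.5 | 0.7 | about no difference | 12% higher; model-based variance about 21% too small |

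With an unstructured covariance, the common-mean model matches the optimal adjustment in all three rows.

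**Step 5: the group main effect.** If visits are weighted equally and the effect d is the same at both later visits, the main effect estimates (0 + d + d)/3 = 2d/3. Simulated power for one arm against control (10 per arm, d = 0.8 SD, equal SDs, unadjusted) at ρ = 0.5 was 29% for the main effect and 42% for the change contrast. At ρ = 0.3 the order reverses: 35% and 32%.

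**The case against.** The strongest reply is that a change contrast is legitimate. It matches the wording of Hypothesis 1 and is unbiased under randomisation. A reader might infer that the planned analysis is biased or invalid; the documents do not support that.

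A second reply is that the covariate list is open, so baseline adjustment is not excluded. This is correct, and it is why the change reading is called an inference. But an open list does not commit the sponsor to adjustment, and the plan would need to state it under either reading.

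Third, the gain is not guaranteed. It depends on a correlation and SDs that the documents do not give, and Steps 3 and 4 show settings where it vanishes or the interval widens slightly. This stands and limits the claim.

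Fourth, a reader might infer that a common pre-intervention mean can be added to the planned random intercept and keep the full 35% to 5% reduction. That needs equal SDs across visits, which nothing in the documents establishes. When SDs rise, this pairing can be less precise than the planned contrast and understate its own error.

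Fifth, a reader might infer that the main effect is always the weaker test. It is not, as Step 5 shows at ρ = 0.3. The 2/3 figure also needs equal visit weights: under reference-cell coding the group coefficient is the pre-intervention difference. Nor does the plan call this trigger its primary test. What stands is that a term averaged over a pre-treatment visit does not answer Hypothesis 1 cleanly.

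**Conclusion.** The concern holds as a point of efficiency and pre-specification. It rests on the text that the pre-intervention outcome is not among the listed terms and that no primary contrast, visit or arm comparison is named. It rests on inference that the pre-intervention visit is a response.

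On that reading, the planned contrast is valid and in large samples never more precise than a baseline-adjusted one. The loss avoided is between 35% and 5% of the variance for correlations from 0.3 to 0.9 with equal SDs, and about zero if SDs rise enough after the first visit. These sizes depend on assumed correlations, SDs and arm sizes, and on complete data. The missing primary contrast depends on none of them and is the firmer half of the point. The plan should be changed, but nothing here shows that its results would be wrong.

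**What to change.** For the primary and secondary endpoints:

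1. Use one of two models.
   - Post-intervention and follow-up as responses, with the pre-intervention value of the same outcome and its interaction with time as covariates.
   - All three visits as responses, with one common pre-intervention mean and an unstructured covariance as the main model. Group × gender must then apply only after the pre-intervention visit, or it brings back a group difference at baseline.
2. Do not pair the common mean with the random intercept alone.
3. Name one primary contrast in advance: the visit, and whether the brace arm, the band arm or both pooled are compared with control.
4. Do not use a group main effect averaged over the pre-intervention visit to trigger post-hoc tests.

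The cost is SAP wording and code; no new data are needed. An unstructured covariance for three visits has six parameters (three variances, three covariances) against two for the random intercept, which costs a few degrees of freedom. If arms are very small and the correlation is near 0.9, or SDs are larger after the intervention, expect little or no gain or a slightly wider interval.
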